### 3. STUDY DESIGN

Research Governance and Integrity Team

This will be a pilot RCT of a financial incentives-based intervention. All CYP will be recruited from London Hospital Emergency Departments (EDs) including: St Mary's Hospital (Imperial College Healthcare NHS Trust); Chelsea and Westminster Hospital (Chelsea and Westminter Hospital NHS Foundation Trust); University College Hospital (University College London Hospital NHS Foundation Trust); Whittington Hospital (Whittington Health NHS Trust; The Royal London Hospital (Barts Health NHS Trust); The Hillingdon Hospital (Hillingdon Hospitals NHS Trust); Royal Brompton Hospital and Evelina Children's Hospital (Guy's and St Thomas' NHS Foundation Trust)

A list of ED attendees will be reviewed every week by the direct care team and those coded for acute asthma who fulfil the eligibility criteria will be identified and sent an automated WhatsApp/SMS message with a link to the study. If they are interested in participating, they will be asked to enter their contact details which will then be shared with the study coordinator. The study coordinator will then contact potential participants with further study information. The link to the study will also be provided on posters which will be displayed in the EDs and on leaflets which will be given to potential participants at the time of their attendance. For those CYP who have a post attack follow up review (either in person, via telephone or video platform) the study will be introduced by the clinician carrying out the review and if the CYP and their parent are interested permission will be obtained to share their contact details with the study coordinator.

No patient identifiable information will be accessed by the research team without prior consent.

If interested in the study, the study coordinator will provide parents with an information sheet as well as an age-appropriate version of the information sheet for CYP. Parents/CYP will have the opportunity to read the information and to ask any questions they have. The consent form, which will involve age-appropriate assent from the CYP, will be completed electronically via a Qualtrics link sent to parents (via email/SMS/WhatsApp). The first study visit will be arranged between 2-12 weeks post presentation to the department with asthma attack.

Fifty participants will be enrolled in the 24-week programme and will be randomly assigned to either the financial incentives-based intervention group or the control group using the online service Sealed Envelope™ which will allocate participants to each group on a 1:1

Research Governance and Integrity Team

basis. Participants will be told which group they have been randomly assigned to during study visit 1.

For all participants, there will be a total of 3 study visits: at baseline (0-weeks), at 12-weeks and at 24-weeks. All study visits will take place at the Children's Clinical Research Facility (CCRF) at St Mary's Hospital, Imperial College Healthcare NHS Trust. Due to the continued COVID-19 restrictions, remote study visits will be offered to participants through Microsoft Teams (joining link will be sent to parents electronically) and an option for study visits to be conducted (by the study coordinator) at participant's homes will also be available, if necessary. However, due to financial constraints, we would not be able to perform FENO remotely, so it will be removed as a secondary outcome measure in this event. All study visits will include the collection of asthma-related clinical data, questionnaire data and adherence data which will be described in detail below.

All CYP's GP's will be informed of the CYP's involvement in the study and a summary of results from each study visit will be sent to the CYP's GP. Information shared in this summary will include ACT score, FENO and adherence data. This summary will also be sent to parents. It is important to note that the study team will not be managing the CYP's asthma or intervening if their adherence is poor – this will be made clear to parents/guardians and CYP and it will be suggested they contact their GP or asthma nurse if there are any concerns throughout the study.

All CYP will be issued with an EMD (Hailie® sensor, Adherium, New Zealand) which attaches to their usual inhalers to electronically record inhaler actuation to provide % adherence data.

All CYP will be required to download the Hailie® associated app on their smartphones and to sync their Hailie® sensor with the associated app, via Bluetooth. The Hailie® sensor will detect medication usage from the attached preventer inhaler and send this to the Hailie® associated app on the CYP's smartphone, also via Bluetooth. The Hailie® associated app will then automatically upload (via WIFI/data connection) the medication usage data to the secure cloud-based Hailie® web portal where the research team will be able to view the data (see image below).

Wi-Fi connection

All CYP will regularly charge and sync their Hailie® device to ensure all data are collected accurately, they will be prompted to do this throughout the study through app notifications. Parents/guardians/CYP will be asked to inform a member of the study team if there are any issues with their EMDs so this can be sorted as soon as possible.

All CYP's Hailie® devices or smartphones will be programmed with both morning and evening audio-visual reminders across the 24-week period. CYP will choose the time of their reminders which will be recorded by the researcher.

There will be no covert adherence monitoring and CYP's adherence data will be downloaded and viewed by the study coordinator before/at each study visit (study visit 2, 12-weeks and study visit 3, 24-weeks). For those in the intervention group, adherence data will also be downloaded and viewed at 4-weeks, 8-weeks to calculate reward amount given only.

At the end of the 24-week programme, all participants will be invited to join a focus group discussion (which will either be in-person at the CCRF or virtually via Microsoft teams) with other CYP from the study. There will be up to 10 participants per focus group and numbers will be dependent upon participant availability. Focus groups with participants from the intervention group and with participants from the control group will be conducted separately. Focus groups will be optional for participants. Parents/guardians will also be invited to take part in an interview in person / via email or telephone to obtain their feedback about the programme. These interviews will be optional and will last approximately 45minutes.

Research Governance and Integrity Team

Interviews will be conducted at study visit 3 and will be conducted in person or virtually (via telephone or via Microsoft Teams, dependent upon preference).

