#### **OUTCOME MEASURES Primary outcome:**

Percentage ICS adherence (measured by EMD record of inhaler actuation%)

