#### Secondary outcomes:

- Proportion of participants achieving good asthma adherence (≥80%)
- Time to next asthma exacerbation needing a course of oral corticosteroids (OCS)
- Total number of severe exacerbations
- Asthma control (Asthma Control Test, ACT)
- Exhaled nitric oxide (FENO)
- Belief in Medicine Questionnaire (BMQ)
- Brief Illness Perceptions Questionnaire (B-IPQ)
- Habit (self-report behavioural automaticity index, SRBAI)
- Autonomous/controlled motivation (adapted from the Treatment Self-Regulation Questionnaire, TSRQ, for the purpose of this study)
- Self-report adherence (Medication Adherence Report Scale for Asthma, MARS-A)

**POPULATION** CYP aged 11-17 years with an asthma diagnosis

ELIGIBILITY

- CYP aged between 11-17 years old
- A doctor diagnosis of asthma
- Presenting to an emergency department (ED) with a severe exacerbation of asthma (defined by ERS/ATS guidelines\*)
- Own their own smartphone (running Android 8 or higher, or iOS 13 or higher)
- Prescribed maintenance inhaled corticosteroids (ICS) (which can include maintenance and reliever therapy (MART)) for at least 6-months.
- Prescribed one of the following inhalers: Clenil, Flixotide, Symbicort, Seretide.
- **DURATION** Up to 24-weeks (participants will also be involved in a focus group at the end of the study period)

\* Severe exacerbation of asthma: Asthma attack requiring a course of systemic corticosteroids (either prednisolone or dexamethasone), or hospital admission 

Research Governance and Integrity Team

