#### **STUDY VISIT 1:**

Prior to any tests, it will be ensured that all parents/CYP understand all the information provided and have electronically signed the informed consent form.

Participants will be given the Hailie® sensor and shown how to use this, as described above. Participants will be assessed and given guidance on their inhaler technique and will be provided with an Asthma UK children's asthma plan (unless already in receipt of an asthma plan, see appendix for plan) which will be conducted by a clinical research nurse.

The following information will be collected from all CYP; demographics, asthma history, asthma adherence (measured by self-report, MARS-A), asthma control (measured by ACT questionnaire, FENO – which will be measured by the child breathing out slowly though a mouthpiece where the nitric oxide from the breath will be measured the sensor and computer) and behavioural/psychological data (measured by BMQ, B-IPQ, SRBAI, TSRQ-adapted for this study).

Participants will be randomly assigned to either the 1) control group (n=25) or to the 2) financial incentives-based intervention group (n=25). Participants will be told which group they have been randomly assigned to during this visit.

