#### 3.1. STUDY OUTCOME MEASURES

Primary outcome:

• ICS adherence (measured by EMD record of inhaler actuation%)

Secondary outcome:

- Proportion of participants achieving good asthma adherence (≥80%)
- Time to next asthma exacerbation needing a course of oral corticosteroids (OCS)
- Total number of severe exacerbations (incident rate ratio)
- Asthma control (measured by asthma control test (ACT))
- FENO
- Habit (measured by Self-Report Behavioural Automaticity Index, SRBAI)
- Belief in Medicines Questionnaire (BMQ)
- Brief Illness Perception Questionnaire (B-IPQ)
- Autonomous/controlled motivation (adapted from the Treatment Self-Regulation Questionnaire, TSRQ)
- Self-report adherence (Medication Adherence Report Scale for Asthma, MARS-A)

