#### 4.2. INCLUSION CRITERIA

Inclusion criteria are:

- Informed consent obtained from parent/guardian and assent from the child.
- Children or young person with doctor diagnosed asthma presenting to Emergency Departments (ED) with a severe asthma exacerbation (as defined by ERS/ATS guidelines).
- Aged between 11 and 17 years old
- Prescribed maintenance inhaled corticosteroids (ICS) (which can include maintenance and reliever therapy (MART)) for at least 6-months.
- Own their own mobile smartphone (running Android 8 or higher, or iOS 13 or higher)
- Prescribed the following inhalers:
  - o Clenil
  - o Flixotide
  - Symbicort
  - $\circ$  Seretide

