#### 7.2 Statistical methods and sample size

As this is a pilot study, a formal sample size calculation is not required. However, the estimated sample size of 50 participants in total is based upon a calculation from unpublished adherence data obtained from Royal Brompton Hospital from 400 children. Mean adherence in the sample was 65% (SD 22%). A Cochrane review of adherence interventions to ICS for asthma found that electronic trackers or reminders led to better adherence of 19% (95% CI 14.47 to 25.26). Based upon this information, to give 80% power to achieve a 19% difference between the intervention group and controls, 21 participants are required per group. The target of 25 per group accounts for participant dropout. This is supported by evidence that as a pilot study, 25 participants per group, with a total of 50 participants is sufficient.

Data analysis will be conducted using the Statistical Package for the Social Services (SPSS). Statistical analysis of quantitative, normally distributed data will be reported with means ± standard deviations (SD) and non-parametric data will be reported as medians with interquartile range. Data will be tested for normality using visual inspection, histograms, and Kolmogorov-Smirnov testing. Parametric tests will be used where possible for normally distributed data and logarithmically transformed data, otherwise appropriate non-parametric tests shall be used. The significance levels for all tests will be set at <0.5.

Categorical data will be reported as proportions. Comparative analysis of variance between 2 groups for continuous data will be performed using the student's t test for normally distributed data and the Mann Whitney U tests for non-normally distributed data and for more than 2 groups the ANOVA or Kruskal Wallis respectively. A comparison of the proportions between groups will be performed using the Pearson Chi 2 tests. Within group analysis the ANOVA test will also be used.

Questionnaire data will be used alongside group comparisons to observe any notable changes or differences between groups.

Qualitative data obtained from the focus groups will be thematically analysed. An independent researcher will aid with the facilitation/analysis of qualitative aspect of the study to ensure there is no bias.

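### Prescribed regimen (MART or separate preventer) can affect the recorded actuation percentage, but the plan neither balances nor adjusts for it: a modest loss of precision, not a bias

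*Combined protocol and SAP*

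**What the plan says.** - **Allocation.** Section 3 names an online service "which will allocate participants to each group on a 1:1" basis, and Study Visit 1 gives the arm sizes: "Participants will be randomly assigned to either the 1) control group (n=25) or to the 2) financial incentives-based intervention group (n=25"). No stratification factor, minimisation factor or block scheme is described.
- **Eligibility.** Section 4.2 admits children on maintenance inhaled corticosteroids, "which can include maintenance and reliever therapy (MART)) for at least 6-months".
- **Primary outcome.** Section 3.1 gives it as "ICS adherence (measured by EMD record of inhaler actuation" %). Section 3 says of the device: "The Hailie® sensor will detect medication usage from the attached preventer inhaler".
- **Counting rule.** None is stated for the percentage: no denominator, no cap, and nothing on as-needed MART puffs. The only cap is on payment, £2 per day, in the description of the intervention arm.
- **Baseline.** The section 6 schedule has a dash for ICS adherence % at visit 1 and a cross at visits 2 and 3.
- **Analysis.** Section 7.2 states: "Comparative analysis of variance between 2 groups for continuous data will be performed using the student's t test" if the data are normally distributed, and otherwise by Mann-Whitney. No covariate is mentioned.

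**The concern.** Under MART one inhaler serves both maintenance and relief, so the sensor on it registers both kinds of use. A relief puff can then stand in for a missed maintenance dose in the record. For a child with a separate reliever, relief use does not reach the sensor on the preventer. Regimen is therefore more than an ordinary prognostic factor: it can act on the primary outcome through the measuring device, and it is known before randomisation.

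With 25 children per arm, chance can put more MART users in one arm. The planned test does not separate the resulting shift from the effect of the incentives. The usual safeguard, adjusting for the baseline value of the outcome, is not available because sensor adherence starts only after visit 1. The third aim (section 2.1) is to inform the power calculation and design of a definitive trial, so a shifted estimate, or an SD that includes regimen variance, would carry forward.

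**Working it through.** **Inputs from the documents.** 25 per arm; SD 22 points; target difference 19 points; 80% power; 21 per group before dropout (section 7.2).

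**Inputs assumed, because the documents do not give them.** p, the share of children on MART: 10% to 50%. D, the difference in mean recorded adherence between MART and separate-preventer children: 10 or 20 points in either direction.

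**1. The plan's own figure.** n = 2 × [22 × (1.960 + 0.842) / 19]² = 21.05 per group. The stated 21 gives 79.9% power by the normal approximation, so it reproduces with two-sided 0.05. (Section 7.2 prints the significance level as <0.5, which would need only 7 per group. That is a separate point.)

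**2. Standard error of the arm difference.** 22 × √(2/25) = 6.2 points.

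**3. Chance imbalance.** With 50p MART children and a 25/25 split, the MART count in one arm is hypergeometric. The SD of the difference in MART share between arms is 2√[p(1−p)]/7. For p = 0.3 this is 2 × 0.458 / 7 = 0.131, or 13.1 percentage points.

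**4. Shift in the estimate.** 95% range = ±1.96 × D × (SD from step 3).

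**5. Gain from adjustment.** Share of variance due to regimen = p(1−p)D²/22². The standard error is multiplied by √(1 − share). For p = 0.3 and D = 20: 0.21 × 400 / 484 = 0.174, and √0.826 = 0.909, a cut of 9%.

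| MART share | SD of share difference | 95% shift, D=10 | 95% shift, D=20 | SE cut, D=10 | SE cut, D=20 |
|---|---|---|---|---|---|
| 10% | 8.6 pp | ±1.7 | ±3.4 | 0.9% | 3.8% |
| 20% | 11.4 pp | ±2.2 | ±4.5 | 1.7% | 6.8% |
| 30% | 13.1 pp | ±2.6 | ±5.1 | 2.2% | 9.1% |
| 50% | 14.3 pp | ±2.8 | ±5.6 | 2.6% | 10.9% |

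With D = 5 the shift is at most ±1.4 points, and at 30% MART the standard error falls by 0.5%. With D = 30 the shift would be ±5.0 to ±8.4 points across these shares.

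**6. How often a large imbalance occurs.** The chance that the arms differ by 5 or more MART children (20 percentage points) is 0.217 with 15 of 50 on MART, 0.258 with 25 and 0.049 with 8. With 15 on MART, the other 78% of allocations differ by 1 or 3 children. At D = 20 that is a shift of 0.8 or 2.4 points.

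**7. Simulation** (8,000 runs per setting, total SD held at 22). Across four settings (D = 20 with 20%, 30% or 50% MART; D = 30 with 30% MART), the planned unadjusted test had type I error of 4.5% to 5.1%. At 30% MART and D = 20:

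| Design | Type I error | Power for 19 points |
|---|---|---|
| As planned | 4.5% | 85% |
| Covariate only | 5.0% | 90% |
| Stratified, no covariate | 3.4% | 86% |
| Stratified plus covariate | 4.9% | 91% |

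The simulated spread of the estimate fell from 6.14 to 5.75 with the covariate alone: 1 − 5.75/6.14 = 6%. This is somewhat below the 9% of step 5, which leaves out the small cost of adjusting for an unbalanced covariate; simulation error also plays a part.

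**The case against.** The strongest objection is that the size is assumed. Neither p nor D is in the documents, and even the sign of D is unknown: relief puffs could raise the count, or MART children could take fewer scheduled doses. This stands. At D = 10 or below the gain is slight, and a claim that the result moves by several points holds only if D is about 20 or more.

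A reader might infer a biased comparison or an invalid test. The documents do not support that. Chance imbalance is random error that the unadjusted test already reflects, as step 7 shows. If the 400 children behind the SD of 22 had a similar regimen mix, this variance is already in the planned figure. The documents do not say whether they did.

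A reader might also infer simple, unrestricted allocation. Section 3 is silent on the set-up, and exactly 25 per arm may point to blocking. Blocks without a regimen stratum would still leave regimen unbalanced.

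Finally, a counting rule could shrink D. The payment rule credits a morning and an evening dose and pays nothing for use beyond that prescribed. If the adherence percentage were scored the same way, D would fall, though a relief puff in the morning or evening window could still register as a dose. The documents do not say how the percentage is scored. This is the more basic gap, and neither stratification nor adjustment closes it.

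**Conclusion.** The point holds as an inexpensive improvement in precision. The documents establish that both regimens are eligible, that the outcome counts actuations of an inhaler that MART children also use for relief, and that the plan neither balances nor adjusts for regimen and has no baseline sensor value. For MART shares of 10% to 50%, the 95% range of the chance shift is about ±2 to ±3 points at D = 10 and ±3 to ±6 points at D = 20, beside a standard error of 6.2 points and a 19-point target. The formula gain from adjustment is about 1–3% and 4–11% of the standard error respectively. All of these figures rest on assumed p and D and on the SD of 22 applying here. Most of the benefit comes from the covariate; stratification adds little to it.

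**What to change.** **Main change.** In section 7.2, replace the two-group test of sensor adherence with a linear model containing arm and prescribed regimen (MART versus separate preventer). Record regimen at visit 1, before allocation. The cost is one data field, one degree of freedom and a regression in place of the t test. The Mann-Whitney fallback must be restated to match, for example as a rank test stratified by regimen.

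**Optional.** If recruitment has not started, which the documents do not state, section 3 may also specify permuted blocks stratified by regimen, always together with the covariate, because stratifying alone makes the test conservative (3.4% in step 7). If MART users are few, an incomplete block could leave the arms uneven by one or two children.

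**Alongside.** State separately how MART actuations enter the adherence percentage: numerator, denominator and any cap. The covariate does not settle this.

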#### 1.2. RATIONALE FOR CURRENT STUDY

In paediatric asthma, there are currently no randomised trials that explore the effectiveness of using financial incentives for improving medication adherence. A US proof-of-concept study that used electronic reminders coupled with financial incentives improved adherence to asthma medications in 12 African American adolescents. Participants were provided with a smartphone and an EMD (with associated App) to provide visual reminders, positive reinforcement (e.g., shooting a basket game and positive text messages when dose is taken) plus rewards (short-term: accessories to decorate personal app avatar and long-term: 1\$ per inhaler dose). Both adherence and asthma control (measured by the asthma control test ACT) improved across the 8-week period.

Similarly, a feasibility study conducted by ourselves found the use of financial incentives to be feasible and acceptable for improving adherence in paediatric asthma. Adolescents diagnosed with asthma, who had poor medication adherence (<80%) and poor asthma control were recruited from an outpatient asthma clinic. Twelve adolescents were invited to take part and 10 were recruited (7 males, 3 females, 12-16 years) to a 24-week intervention that consisted of eight weeks of electronic reminders and financial incentives related to their adherence (£1 per morning dosage, £1 per evening dosage, capped at £2 per day). Eight out of 10 adolescents provided adherence measurements up to the final study visit. Three adolescents successfully paired their mobile app and EMD up to the final study visit which was associated with improved adherence. The 7 adolescents unable to pair their mobile app and EMD had no change in adherence. Overall, adherence did not significantly change. Exit interviews with adolescents revealed reminders and incentives were welcomed but issues with the technology was frustrating. Adolescents also commented that the intervention was useful by promoting self-monitoring and increasing motivation to take medication.

These findings within asthma warrant the further exploration of this intervention design using financial incentives with the inclusion of a larger sample size and randomisation. In addition, to explore the potential mediators of sustained behaviour change, motivation and the key feature of habit, automaticity, will be tracked in this study.

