#### 2. Financial incentives-based intervention (n=25):

Participants will be provided with a summary information sheet regarding the intervention programme and will be given the time to read through this and to ask any questions.

Participants will receive gain-framed financial incentives based upon frequency of ICS adherence (£1 per morning dose and £1 per evening dose / maximum £2 per day regardless of prescription / £168 maximum per participant during the 12-week period). Participants will not be able to earn more money by taking their inhaler more than

Research Governance and Integrity Team

prescribed. Participants will be able to see how much money they have earned in real-time by an in-app totaliser which increases by £1 every time the EMD recognises the morning or evening dose has been taken when the Hailie® sensor and the app are synced. Participants will receive their money (in form of an 'One4all' voucher) in 4-weekly instalments (at 4weeks, 8-weeks, and 12-weeks / total £56 per each 4-week period). The 'One4all' voucher will be sent to the child's smartphone via text message. Participants will receive regular messages updating them on their progress in terms of financial incentives. Messages will be delivered as notifications via the app and will be seen on participants' smartphones. Participants will also be able to monitor their adherence in an in-app calendar that follows a traffic-light coding system to display daily adherence (e.g., red if no doses taken, orange if some taken and green if all inhaler puffs are taken per day).

During this intervention period, participant's Hailie® adherence data will also be downloaded and viewed via the Hailie® web portal virtually by the study coordinator at 4-weeks and 8-weeks (in addition to being downloaded at 12-weeks, study visit 2 and 24-weeks, study visit 3) to assess reward amount given.

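### Sensor data are viewed at weeks 4 and 8 in the intervention arm only, so capture of the primary outcome could differ by arm, and section 7.2 has no rule for days without data

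*Combined protocol and SAP*

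**What the plan says.** Section 3.1 gives the primary outcome only as "ICS adherence (measured by EMD record of inhaler actuation", expressed as a percentage. Data reach the research team by Bluetooth from sensor to app and then by upload to the web portal (section 3).

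For both arms, section 3 plans downloads at visits 2 and 3 (weeks 12 and 24), app notifications to charge and sync, and a request that families report device faults. The general instruction is: "All CYP will regularly charge and sync their Hailie® device to ensure all data are collected accurately".

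Two things apply to the intervention arm alone:

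- Its "adherence data will also be downloaded and viewed at 4-weeks, 8-weeks to calculate reward amount given only".
- Its in-app total goes up by £1 "every time the EMD recognises the morning or evening dose has been taken when the Hailie® sensor and the app are synced". It also receives progress messages and a traffic-light calendar of daily adherence. Section 3, Study Visit 2, withdraws all of these at week 12.

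Controls receive usual care and reminders and are asked to do nothing further. Section 7.2 has no rule for unsynced, missing or device-failure days and does not plan to report data capture by arm.

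On pairing, section 1.2 reports from the sponsor's own feasibility study: "The 7 adolescents unable to pair their mobile app and EMD had no change in adherence". The same paragraph says that 8 of the 10 gave adherence measurements up to the final visit.

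**The concern.** During weeks 0 to 12 the intervention arm has three signals of a failed sensor that controls lack: a total that stops rising, a calendar that shows no doses, and a coordinator looking at the record at weeks 4 and 8. In controls, a sensor that falls silent soon after visit 1 could stay unseen by the team until week 12, unless the child or parent notices and reports it.

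Syncing a sensor is not the same as using an inhaler. If capture is better in one arm, part of the observed difference is measurement rather than adherence. The direction depends on a scoring choice that section 7.2 does not make. Under section 7.1 the coordinator who views the data also runs the analysis, so that choice could be made after the data are seen.

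The proportion reaching 80% adherence comes from the same record. Weeks 12 to 24 are also exposed: once the total and calendar are withdrawn, a fall in syncing could be read as a fall in adherence, which bears on Objective 1. Aim 3 would carry any bias into the power calculation for the definitive trial.

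**Working it through.** **Inputs from section 7.2:** mean adherence 65%, SD 22%, target difference 19 points, 80% power, 21 per group, 25 per group with dropout. No significance level is stated for the sample size, so two-sided 0.05 is assumed. All capture rates below are assumptions, because the documents give none.

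**Step 1. The plan's own figure.** Section 7.2 says that "to give 80% power to achieve a 19% difference between the intervention group and controls, 21 participants are required per group". Check: n = 2 × [22 × (1.96 + 0.84) / 19]² = 21.05 per group. The stated 21 reproduces, and this point does not dispute it.

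**Step 2. Uncaptured days scored as zero.** Observed adherence = true adherence × share of days captured. With no true effect, false difference = 65 × capture gap. With 25 per arm, SE = 22 × √(2/25) = 6.22, and the chance of a significant result is Φ(d/SE − 1.96) + Φ(−d/SE − 1.96).

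| Assumed capture gap | False difference d | Share of 19 | Chance of a significant result |
|---|---|---|---|
| 0 | 0 | 0% | 5% |
| 5 points | 0.05 × 65 = 3.25 | 17% | 8% |
| 10 points | 0.10 × 65 = 6.5 | 34% | 18% |
| 20 points | 0.20 × 65 = 13.0 | 68% | 55% |

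To produce the whole 19 points, the gap would have to be 19/65 = 29 points.

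**Step 3. Uncaptured days dropped.** Suppose 20% of control days are uncaptured, true adherence on those days is 40%, overall control adherence is 65%, and the intervention arm is fully captured. Controls then read (65 − 0.20 × 40) / 0.80 = 57 / 0.80 = 71.25, which understates the benefit by about 6 points.

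**Step 4. The two scorings on the same case.** With the Step 3 assumptions, scoring those days as zero makes controls read 65 − 0.20 × 40 = 57, which overstates the benefit by 8 points. The truth (65) lies between 57 and 71.25. This figure is 8 rather than 13 because Step 2 takes adherence on uncaptured days to be the same as on other days.

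**Step 5. What the feasibility study shows.** Three of 10 stayed paired and 8 of 10 gave data to the final visit. At least 8 − 3 = 5 of the 7 unpaired adolescents therefore still supplied adherence data.

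**The case against.** The strongest reply is that the outcome downloads at weeks 12 and 24, the app prompts and the fault reporting are common to both arms. The week 4 and 8 views are described as serving the reward only, and nothing says that the coordinator acts on an empty record. The sensor records actuations and syncing transfers them, so a sensor unsynced at week 4 but synced by week 12 may lose nothing. This stands, and it is why unequal capture is a risk rather than an expected result. It does not remove the risk. A silent sensor is still visible to someone viewing the record, the documents do not give the sensor's memory capacity, the protocol does not commit to reading stored data directly, and visits may be remote.

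Three stronger readings are tempting, and the documents do not support them:

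- A reader might infer from 7 failures in 10 that days without data will be common. Step 5 shows that failed pairing did not usually mean lost data. All 10 were also in an incentive programme with no unpaid comparison group, so that study cannot show that payment improves syncing.
- A reader might infer that children are paid only for synced doses. The text ties the displayed total to syncing and reads weeks 4 and 8 from the portal, but it nowhere says that a dose synced late goes unpaid.
- A reader might infer that the bias is as large as the effect sought. The figures above are 3 to 13 points, and 19 would need a 29-point gap.

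**Conclusion.** The point holds as a risk of arm-dependent measurement that is cheap to reduce. The difference in checks, and in the signals that reveal a failed sensor, is in the text, and the analysis section does nothing to contain it. For assumed capture gaps of 5 to 20 percentage points, zero-scoring creates about 3 to 13 points of false benefit, and dropping days can hide about 6 points in the case worked above. These sizes rest on 65% adherence (section 7.2), on poorer capture in controls, on the assumed gaps and, for the dropped-day case, on an assumed 40% adherence on the lost days. If capture is equal in the two arms and unrelated to adherence, there is no false difference. The documents do not show that capture will differ, so the plan should be changed to prevent and measure the problem rather than be treated as biased.

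**What to change.** **Section 3.** Check sync status on the portal at weeks 4 and 8 in both arms, and send the same scripted sync prompt to any child without a recent upload. In controls, use the check for sync status only. At visits 2 and 3, sync the sensor or read its stored data in both arms before any day is declared uncaptured. At a remote visit, have the child sync during the call.

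**Section 7.2.** Define a day with data. Treat confirmed device-failure or uncaptured days as missing in the primary analysis. Report days with data by arm for weeks 0–12 and 12–24, and give a sensitivity analysis that scores those days as zero. Both results are needed, because the two scorings can err in opposite directions. Capture by arm also answers Aim 2 on the feasibility of outcome assessment.

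**Cost.** About 25 × 2 = 50 extra portal look-ups by the same coordinator, plus some wording. Controls get slightly more contact, which could itself nudge their adherence. The total and calendar stay in one arm as part of the intervention, so some difference in syncing may remain. The capture report and sensitivity analysis are there to show it.
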